Appendix 2 Schedule of *Activities* for Recurrent Influenza

	Confirm Influenza A Day -3 to Day 1	D1	D2	D3	D4	D5	D6	D7 (±1)	D8-13	D14 (±2)
Rapid antigen test (RAT) or PCR test ^a	x									
Confirm onset of recurrent flu symptoms	x									
Concomitant medications ^b		x	x	x	x	x	x	x	x	x
Vital signs ^c		x		x				x		
Electrocardiogram (12-lead) ^d		x		x				x		
Complete physical examination ^e		x								
Limited, symptom-directed physical examination/symptom assessment ^f				x				x		
Weight ^g		x		x				x		
Adverse events		x	x	x	x	x	x	x	x	x
Hematology ^h		x		x				x		
Chemistry panel ^h		x		x				x		
Coagulation panel ^h		x		x				x		
Urinalysis ⁱ		x		x				x		
██████████ ██████████		x		x		x		x		
Anti-MHAA4549A antibodies (ATA)								x		
Serum for MHAA4549A PK measurements								x		
Telephone visit to assess safety			x							x
Symptom Diary ^k		x	x	x	x	x	x	x	x	x

AE = adverse event; D = day; NSAID = non-steroidal anti-inflammatory drug; PCR = polymerase chain reaction; RAT = rapid antigen test; RBC = red blood cell; WBC = white blood cell.

Notes: Days 1, 3, 5, 7 (shaded) will be clinic visits.

Patients with RECURRENT influenza symptoms between Day 14 and Day 100 [defined by at least 1 constitutional symptom (headache, myalgias, fever, chills, fatigue, anorexia, nausea and 1 respiratory symptom (cough, sore throat, rhinorrhea)] will be evaluated for 14 days. These patients must still complete *telephone* follow-up visits at Days 30 and 100 from initial randomization (see [Appendix 1](#)):

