3. STUDY DESIGN

3.1 DESCRIPTION OF STUDY

3.1.1 Overview of Study Design

This is a randomized, double-blind, placebo-controlled study (GV29893) designed to assess the safety *and tolerability*, efficacy, and pharmacokinetics of MHAA4549A compared to placebo when administered to approximately 141 otherwise healthy patients with acute uncomplicated seasonal influenza A. This study will inform the safety of MHAA4549A in the natural influenza infection setting.

Patients who are eligible for enrollment will be randomized in a 1:1:1 ratio into three treatment groups: a single IV dose of 3600 mg MHAA4549A, a single IV dose of 8400 mg MHAA4549A, or a single IV dose of placebo. Study drug administration will begin within 72 hours (3 days) of onset of influenza-like illness (as defined in the inclusion criteria, Section 4.1.1) and all patients will be followed for a minimum of 100 days from randomization. After study discharge, all drug-related serious adverse events will continue to be reported to the Sponsor. Randomization will be stratified by

onset of influenza-like illness (≤ 36 hours and > 36 hours) and type of influenza test used for enrollment (rapid PCR or rapid antigen test). A permuted block randomization method will be used to obtain an approximate 1:1:1 ratio of patients in the 3600 mg MHAA4549A, 8400 mg MHAA4549A, or placebo groups within each stratum.

A rapid PCR test or rapid antigen test will be used as an aid in the diagnosis of influenza A infection and serve as the basis for satisfying study entry requirements. The intent-to-treat (ITT) population will include all patients randomized who received study medication. A central quantitative PCR test will be performed on Day 1 virology samples to confirm influenza A infection and define the intent-to-treat infected (ITTI) population for analyses.

If a patient develops new symptoms of influenza (as defined in the inclusion criteria, Section 4.1.1) between Days 14 and 100, consistent with recurrent influenza infection (reinfection after initial influenza symptoms completely resolved), he/she should immediately inform site study personnel. A rapid PCR test or rapid antigen test will be performed as soon as possible, preferably within 72 hours of influenza symptom onset.

[figure not shown]
[REDACTED]

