5.3.1 Adverse Event Reporting Period

Investigators will seek information on adverse events at each patient contact. All adverse events, whether reported by the patient or noted by study personnel, will be recorded in the patient's medical record and on the Adverse Event eCRF.

After informed consent has been obtained **but prior to initiation of study drug**, only serious adverse events caused by a protocol-mandated intervention (e.g., invasive procedures such as biopsies, discontinuation of medications) should be reported (see Section 5.4.2 for instructions for reporting serious adverse events).

After initiation of study drug, all adverse events will be reported until study *completion* at the Day 100 visit or until an Early Discontinuation visit. After this period, the investigator should report any serious adverse events that are believed to be related to prior study drug treatment (see Section 5.6).

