5.5.2 Sponsor Follow-Up

For serious adverse events, adverse events of special interest, and pregnancies, the Sponsor or a designee may follow up by telephone, fax, electronic mail, and/or a monitoring visit to obtain additional case details and outcome information (e.g., from hospital discharge summaries, consultant reports, autopsy reports) in order to perform an independent medical assessment of the reported case.

5.6 *ADVERSE EVENTS THAT OCCUR AFTER THE ADVERSE EVENT REPORTING PERIOD*

The Sponsor should be notified if the investigator becomes aware of any serious adverse event that occurs after the end of the adverse event reporting period (defined as 100 days after study drug administration), if the event is believed to be related to prior study drug treatment. *These events should be reported through the use of the Adverse Event eCRF. However, if the EDC system is not available, the investigator should report these events directly to the Sponsor or its designee, either by faxing or by scanning and emailing the Serious Adverse Event/Adverse Event of Special Interest Reporting Form using the fax number or email address provided to investigators.*

5.7 *EXPEDITED REPORTING TO HEALTH AUTHORITIES, INVESTIGATORS, INSTITUTIONAL REVIEW BOARDS, AND ETHICS COMMITTEES*

The Sponsor will promptly evaluate all serious adverse events and adverse events of special interest against cumulative product experience to identify and expeditiously communicate possible new safety findings to investigators, IRBs, ECs, and applicable health authorities based on applicable legislation.

To determine reporting requirements for single adverse event cases, the Sponsor will assess the expectedness of these events using the following reference document:

- MHAA4549A Investigator's Brochure

The Sponsor will compare the severity of each event and the cumulative event frequency reported for the study with the severity and frequency reported in the applicable reference document.

Reporting requirements will also be based on the investigator's assessment of causality and seriousness, with allowance for upgrading by the Sponsor as needed.

Certain adverse events are anticipated to occur in the study population at some frequency independent of study drug exposure and will be excluded from expedited reporting. These anticipated events include, but are not limited to, the following:

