6. STATISTICAL CONSIDERATIONS AND ANALYSIS PLAN

The database will be cleaned and locked when all patients have completed the study (Day 100) or discontinued.

The primary objective of this study is to characterize the safety and tolerability of a single dose of MHAA4549A as compared to placebo when administered in otherwise healthy patients with acute uncomplicated seasonal influenza A. Statistical summaries will be descriptive in nature (e.g., means, standard deviations, and percentiles). Patients will be grouped according to treatment actually received, and any patients who receive any amount of MHAA4549A or placebo will be included in the analyses.

All secondary efficacy analyses will be conducted according to the intent-to-treat principle and will include all patients who meet the following condition with patients allocated to the treatment arm to which they were randomized:

- Confirmation of influenza A from Day 1 pre-dose samples using a central PCR (to exclude false positives from local tests)

No formal hypothesis testing will be done in this study. As a result, no adjustment for type 1 error will be made to account for the multiplicity of analyses.

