Appendix 2 (cont'd)

Schedule of *Activities* for Recurrent Influenza

Confirm influenza A (+ or -).

If either the RAT or PCR is positive, the patient will follow the schedule of *activities* and start at Day 1. If the patient tests negative by RAT, the results will be confirmed by RT-PCR. The patient will follow the assessments in Appendix 2, until a negative PCR result for influenza is confirmed.

^a Sample collection may involve a nasal swab or a nasopharyngeal swab, depending on the diagnostic platform *at the site*.

^b See exclusion criteria for prohibited therapies

^c Vital signs include temperature (*oral*), respiratory rate, heart rate, systolic blood pressure, and diastolic blood pressure. Temperature should be measured using the same methodology throughout the study and should be measured prior to administration of any antipyretic drugs. Temperature, blood pressure, respiratory rate, and heart rate will be completed after the patient has been in a seated or supine position for > 5 minutes.

^d Patient should rest in a supine position for 10 minutes prior

^e Complete physical examination includes evaluations of general appearance of head, eye, ear, nose, and throat, cardiovascular, dermatological, musculoskeletal, respiratory, gastrointestinal, genitourinary, and neurological systems. Changes from any prior examination should be recorded. New or worsened abnormalities should be recorded as AEs, if appropriate.

^f Limited, symptom-directed physical examination includes, at a minimum, evaluation of general appearance, dermatological examination of the injection sites, evaluations directed by patient-reported symptoms, and any other evaluations that the investigator deems clinically relevant. Changes from any prior examination should be recorded. New or worsened abnormalities should be recorded as AEs.

^g Weight will be recorded in kilograms.

^h Local laboratory measurements should be utilized, Lipase will be reflexively assessed on all samples with amylase > ULN.

ⁱ Urinalysis includes pH, specific gravity, glucose, protein, ketones, blood, bilirubin, nitrite, and leukocyte esterase. Microscopic examination (e.g., sediment, RBCs, WBCs, casts, crystals, epithelial cells, bacteria) will be performed if clinically indicated. *Day 1, 3, 7 samples will be collected locally and centrally.*

^j

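### Adverse event reporting and completion close at a Day 100 contact that may fall on Day 93, and neither they nor database lock wait for a 14-day recurrence schedule that can start as late as Day 100

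*Combined protocol and SAP*

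**What the plan says.** **Length of follow-up.** Section 3.1.1 states that "all patients will be followed for a minimum of 100 days from randomization". Section 3.4.2 sets a 100-day horizon for reinfection or relapse and for influenza-related hospitalization. Section 3.2 gives a duration per subject of about 14 weeks. In Appendix 1 the last contact is a telephone call in the Day 100 column, with a ±7-day window.

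**Closing rules.**
- Section 4.6.4: a patient has completed once all visits through Day 100 are done.
- Section 5.2.1: adverse events are monitored from enrollment through Day 100 or early discontinuation.
- Section 5.3.1: adverse events are reported until completion "at the Day 100 visit or until an Early Discontinuation visit". After that, only serious events believed related to study drug are reported.
- Section 5.4.2.2: serious events and events of special interest are reported until the patient completes at Day 100 or leaves early.
- Section 5.6 uses a calendar definition instead of the visit: "the end of the adverse event reporting period (defined as 100 days after study drug administration".
- Section 6: "The database will be cleaned and locked when all patients have completed the study (Day 100) or discontinued".

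**Recurrent influenza.** Appendix 2 covers "Patients with RECURRENT influenza symptoms between Day 14 and Day 100", who "will be evaluated for 14 days". Its first column is "Confirm Influenza A Day -3 to Day 1". In the notes, "If either the RAT or PCR is positive, the patient will follow the schedule of" activities from recurrence Day 1; a patient negative on the antigen test continues only until PCR confirms the negative. Clinic visits are on recurrence Days 1, 3, 5 and 7, with ATA and PK on Day 7. Adverse events, concomitant medications and diary run to Day 14 (±2), when there is a telephone call. These patients must still complete the Day 30 and Day 100 calls.

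**The concern.** Two sets of rules about when a patient's data collection ends do not fit together.

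First, a site that uses the early edge of the Appendix 1 window completes the patient on Day 93. Section 5.3.1 then closes adverse event reporting, although Sections 3.1.1, 3.4.2 and 5.6 all run to 100 days.

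Second, a recurrence can start on any day up to Day 100 and carries 14 days of assessments, while every closing rule is fixed at Day 100.

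Safety is the primary objective and re-infection rate is a secondary one. If the rules are applied as written, two sites with the same patient could report different adverse events. The database could also be locked, for the last patients in, while a recurrence schedule is still running. Section 6.5 allows no imputation other than censoring in time-to-event analyses, so a patient called early simply has less observed time in endpoints reported as proportions.

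**Working it through.** **Inputs.** Recurrence window Day 14 to Day 100 (Appendix 2): 100 − 14 + 1 = 87 possible start days. Evaluation length 14 days, so recurrence Day 14 is start + 13 and recurrence Day 7 is start + 6. Visit windows: ±2 on recurrence Day 14, ±1 on recurrence Day 7, ±7 on Day 100. Confirmation lag up to 3 days (Appendix 2). I take study Day 100 as the 100-day mark, as the plan does; counting strictly from dosing on Day 1 shifts this by one day and does not change the argument.

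**1. The plan's own figure.** 100/7 = 14.3 weeks, or (100 + 3)/7 = 14.7 weeks with 72 hours of screening. The stated duration of about 14 weeks is reproduced, but only with no recurrence follow-up beyond Day 100.

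**2. Early final contact.** 100 − 7 = Day 93. Days 94 to 100 then have no scheduled contact: 7 of the 87 days in the recurrence window (7/87 = 8%). An unrelated serious adverse event on Day 97, after a Day 93 call, is inside the reporting period under Section 5.6 and outside it under Section 5.3.1.

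**3. Overrun of the recurrence schedule.** With final contact on day C, the last start whose recurrence Day 14 fits is C − 13, and the last whose Day 7 sample fits is C − 6. Onset is counted as recurrence Day 1.

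| Final contact C | Last start with Day 14 on or before C | Starts that overrun | Same, using the −2 window | Starts with Day 7 sample after C |
|---|---|---|---|---|
| Day 93 | 93 − 13 = 80 | 20/87 = 23% | 18 | 13 |
| Day 100 | 100 − 13 = 87 | 13/87 = 15% | 11 | 6 (Days 95–100) |
| Day 107 | 107 − 13 = 94 | 6/87 = 7% | 4 | 0 |

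Using the −1 window on recurrence Day 7, the last column becomes 12, 5 and 0.

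**4. Example.** Recurrence Day 1 is study Day 98 and the final call is on Day 100. Appendix 2 puts the ATA/PK sample on 98 + 6 = Day 104 and collects adverse events to 98 + 13 = Day 111. An unrelated serious adverse event on Day 105 is collected under Appendix 2, but Sections 5.3.1 and 5.4.2.2 closed reporting on Day 100.

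**5. Longest case.** Onset on Day 100 with a 3-day lag gives recurrence Day 1 on Day 103, Day 14 on 103 + 13 = Day 116, and Day 118 with the +2 window. That is 118/7 = 16.9 weeks after dosing, or (118 + 3)/7 = 17.3 weeks with screening.

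**The case against.** The strongest reply is that nothing stops the follow-up. A reader might infer that late recurrences cannot be followed; the documents do not support that. Appendix 2 requires the 14 days without a calendar limit, Section 3.1.1 sets only a minimum, and the Day 100 call is required in addition to the recurrence schedule. Section 5.5.1 has the investigator follow each adverse event to resolution or stability, and Sections 5.3.1 and 5.6 keep related serious events reportable afterwards.

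A reader might also infer that the Day 7 ATA sample is lost after Day 100. It is not: Section 6.9 expressly exempts recurrence Day 7 from its bar on post-dose samples, and Section 5.1.1.1 says post-dosing ATA will be measured in recurrent patients.

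The overrun is also light. Clinic visits, laboratory tests, ECG and sampling end at recurrence Day 7. After that come adverse events, concomitant medications, a diary that can stop at symptom resolution, and one call. The Day 100 window is symmetric and applies to all blinded arms, so no bias between arms is shown.

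All of this stands, and it limits the point to the closing rules. It does not remove the conflict. Section 5.5.1 concerns the follow-up of events, not how long new ones are reported, and the provision for late events leaves out unrelated serious events. No section says that completion or lock waits for an open recurrence schedule.

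**Conclusion.** The point holds as a conflict between stated rules. A Day 93 contact contradicts the 100-day minimum, the 100-day endpoint horizon and the 100-day reporting period. Separately, adverse event reporting, completion and lock do not wait for a recurrence schedule that the plan itself requires.

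The percentages rest on nominal days with onset as recurrence Day 1, before visit windows. It is tempting to read 15% or 23% as a share of recurrences or patients. That would need a recurrence rate and its timing, which the documents do not give; for a seasonal infection a constant rate over the window cannot be assumed. The number of patients is probably small.

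The re-infection proportion is affected only by early final contact. A case counts once identified, so an unfinished 14-day course does not change it. After a Day 93 call, a recurrence on Days 94 to 100 comes to light only if a patient already counted as complete reports it. Sample size and the primary analysis method are unaffected. The correction is worth making because two readings of the same protocol give different reportable safety data, and it is cheap.

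**What to change.** 1. In Appendix 1, change the Day 100 window from ±7 to 0/+7.
2. In the synopsis (end and length of study) and Sections 3.2, 4.6.4, 5.2.1, 5.3.1, 5.4.2.2, 5.6 and 6, define completion, the end of adverse event reporting and database lock by the later of Day 100 and the recurrence Day 14 contact, for any recurrence with onset by Day 100. Use the same wording in each place, and say whether Day 100 means the calendar day or the contact, since these can still differ by up to 7 days under a 0/+7 window.
3. Add to the stated duration that a patient with a late recurrence may be followed longer.

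**Cost.** An amendment of wording, with no new assessment. The earliest permitted final contact moves from Day 93 to Day 100, so up to 7 days later for any patient; the latest stays at Day 107. For the few patients in Appendix 2 at that time, follow-up may run up to about 18 days past Day 100 (118 − 100), and lock may wait that long if one of them is among the last enrolled.

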Appendix 2 (cont'd)

Schedule of *Activities* for Recurrent Influenza

Confirm influenza A (+ or -).

If either the RAT or PCR is positive, the patient will follow the schedule of *activities* and start at Day 1. If the patient tests negative by RAT, the results will be confirmed by RT-PCR. The patient will follow the assessments in Appendix 2, until a negative PCR result for influenza is confirmed.

^a Sample collection may involve a nasal swab or a nasopharyngeal swab, depending on the diagnostic platform *at the site*.

^b See exclusion criteria for prohibited therapies

^c Vital signs include temperature (*oral*), respiratory rate, heart rate, systolic blood pressure, and diastolic blood pressure. Temperature should be measured using the same methodology throughout the study and should be measured prior to administration of any antipyretic drugs. Temperature, blood pressure, respiratory rate, and heart rate will be completed after the patient has been in a seated or supine position for > 5 minutes.

^d Patient should rest in a supine position for 10 minutes prior

^e Complete physical examination includes evaluations of general appearance of head, eye, ear, nose, and throat, cardiovascular, dermatological, musculoskeletal, respiratory, gastrointestinal, genitourinary, and neurological systems. Changes from any prior examination should be recorded. New or worsened abnormalities should be recorded as AEs, if appropriate.

^f Limited, symptom-directed physical examination includes, at a minimum, evaluation of general appearance, dermatological examination of the injection sites, evaluations directed by patient-reported symptoms, and any other evaluations that the investigator deems clinically relevant. Changes from any prior examination should be recorded. New or worsened abnormalities should be recorded as AEs.

^g Weight will be recorded in kilograms.

^h Local laboratory measurements should be utilized, Lipase will be reflexively assessed on all samples with amylase > ULN.

ⁱ Urinalysis includes pH, specific gravity, glucose, protein, ketones, blood, bilirubin, nitrite, and leukocyte esterase. Microscopic examination (e.g., sediment, RBCs, WBCs, casts, crystals, epithelial cells, bacteria) will be performed if clinically indicated. *Day 1, 3, 7 samples will be collected locally and centrally.*

^j

^k The symptom diary and temperature (*oral*) should be completed two times daily: when you first wake up in the morning (before getting out of bed) and about 12 hours later, up to Day 14 or until resolution of symptoms (*defined as a total symptom score of 0-1 for 24 hours without use of symptom relief medications*). Temperature should be taken before administration of acetaminophen/paracetamol and/or NSAIDs.

Appendix 3

DAIDS Toxicity Grading Tables for Clinical Abnormalities

From the FDA Guidance document 'Toxicity Grading Scale for Healthy Adult and Adolescent Volunteers Enrolled in Preventative Vaccine Clinical Trials' (September 2007)

Vital Signs ^a	Mild (Grade 1)	Moderate (Grade 2)	Severe (Grade 3)	Potentially Life Threatening (Grade 4)
Fever (°C) ^b (°F)*	38.0–38.4 100.4–101.1	38.5–38.9 101.2–102.0	39.0–40.0 102.1–104.0	>40 >104
Tachycardia – beats per minute	101–115	116–130	> 130	ER visit or hospitalization for arrhythmia
Bradycardia – beats per minute ^c	50–54	45–49	< 45	ER visit or hospitalization for arrhythmia
Hypertension (systolic) – mmHg	141–150	151–155	> 155	ER visit or hospitalization for malignant hypertension
Hypertension (diastolic) – mmHg	91–95	96–100	> 100	ER visit or hospitalization for malignant hypertension
Hypotension (systolic) – mmHg	85–89	80–84	< 80	ER visit or hospitalization for hypotensive shock
Respiratory Rate – breaths per minute	17–20	21–25	> 25	Intubation

^a Subject should be at rest for all vital sign measurements.

^b Oral/tympanic temperature; no recent hot or cold beverages or smoking.

^c When resting heart rate is between 60–100 beats per minute. Use clinical judgment when characterizing bradycardia among some healthy subject populations, for example, conditioned athletes.

Appendix 3 (cont'd)

DAIDS Toxicity Grading Tables for Clinical Abnormalities

Systemic (General)	Mild (Grade 1)	Moderate (Grade 2)	Severe (Grade 3)	Potentially Life Threatening (Grade 4)
Nausea/vomiting	No interference with activity or 1–2 episodes/24 hours	Some interference with activity or >2 episodes/24 hours	Prevents daily activity, requires outpatient IV hydration	ER visit or hospitalization for hypotensive shock
Diarrhea	2–3 loose stools or <400 g/24 hours	4–5 stools or 400–800 g/24 hours	5 or more watery stools or >800 g/24 hours or requires outpatient IV hydration	ER visit or hospitalization
Headache	No interference with activity	Repeated use of non-narcotic pain reliever >24 hours or some interference with activity	Significant; any use of narcotic pain reliever or prevents daily activity	ER visit or hospitalization
Fatigue	No interference with activity	Some interference with activity	Significant; prevents daily activity	ER visit or hospitalization
Myalgia	No interference with activity	Some interference with activity	Significant; prevents daily activity	ER visit or hospitalization

g=gram; IV=intravenous.

Systemic Illness	Mild (Grade 1)	Moderate (Grade 2)	Severe (Grade 3)	Potentially Life Threatening (Grade 4)
Illness or clinical adverse event (as defined according to applicable regulations)	No interference with activity	Some interference with activity no requiring medical intervention	Prevents daily activity and requires medical intervention	ER visit or hospitalization

Appendix 4

DAIDS Toxicity Grading Tables for Laboratory Abnormalities ^a

HEMATOLOGY				
	Grade 1	Grade 2	Grade 3	Grade 4
Hemoglobin	9.5–10.5 g/dL	8.0–9.4 g/dL	6.5–7.9 g/dL	< 6.5 g/dL
Absolute Neutrophil Count	1,000–1,500/mm ³	750–999/mm ³	500–749/mm ³	< 500/mm ³
*Platelets	125,000–140,000/mm ³	100,000–124,999/mm ³	25,000–99,999/mm ³	< 25,000/mm ³
WBCs	11,000–13,000/mm ³	13,000–15,000/mm ³	15,000–30,000/mm ³	> 30,000 or < 1,000/mm ³
*Lymphocytes Decrease – cell/mm ³	750–1,000	500–749	250–499	< 250
*Eosinophils – cell/mm ³	650–1500	1501–5000	> 5000	Hypereosinophilic
Abnormal Fibrinogen	Low: 100–200 mg/dL High: 400–600 mg/dL	Low: < 100 mg/dL High: > 600 mg/dL	Low: < 50 mg/dL	Fibrinogen associated with gross bleeding or with disseminated coagulation
Fibrin Split Product	20–40 mcg/mL	41–50 mcg/mL	51–60 mcg/mL	> 60 mcg/mL
Prothrombin Time (PT)	1.01–1.25 × ULN	1.26–1.50 × ULN	1.51–3.0 × ULN	> 3 × ULN
Activated Partial Thromboplastin Time (APTT)	1.01–1.66 × ULN	1.67–2.33 × ULN	2.34–3 × ULN	> 3 × ULN
Methemoglobin	5.0–9.9%	10.0–14.9%	15.0–19.9%	> 20.0%

ADL = Activities of Daily Living; CPK = creatine phosphokinase; Dec = Decreased; dl = deciliter; g = gram; IV = Intravenous; LLN = Lower limit of normal; mcg = microgram; mm = millimeter; Mod = Moderate; Req = Required; Rx = Therapy; SGOT = serum glutamic oxaloacetic transaminase; SGPT = serum glutamic pyruvic transaminase; ULN = Upper limit of normal.

^a Adapted from Division of Microbiology and Infectious Diseases (DMID) Adult Toxicity Table November 2007 DRAFT and FDA Guidance document 'Toxicity Grading Scale from Healthy Adult and Adolescent Volunteers Enrolled in Preventative Vaccine Clinical Trials

